### 13.2 Sample Size Determination

Approximately 850 subjects will be treated with CNTX-4975-05. This sample size was chosen based on the need to fulfill safety requirements for regulatory review.

#### 13.3 Analysis Populations

The following analysis populations are planned for this study: The following analysis populations are planned for this study:

- Safety: all subjects who receive any amount of planned CNTX-4975-05.
- Intent-to-Treat (ITT): all enrolled subjects.

Membership in the analysis populations will be determined prior to database lock.

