#### **Injection of CNTX-4975-05:**

ALL subjects are required to be administered an IA injection of a full 15 mL of lidocaine (without epinephrine) (1% or 2%, depending on the assigned treatment regimen) to ensure: 1) the local targeted concentration of CNTX-4975 in the joint; 2) distension of the joint capsule to improve access of CNTX-4975 to the joint space; and 3) to provide some analgesia. The full 15 mL of lidocaine (without epinephrine) and the full 2 mL of CNTX-4975-05 must be injected into the knee joint, as directed. The 5 flexion-extension moves of the knee after IA CNTX-4975-05 is injected into the knee also improve access of CNTX-4975 to the entire joint space. The lidocaine may have some modest effect on pain, but the concentration and dispersion of CNTX-4975 into the joint are the primary reasons for lidocaine use.

The use of ultrasound for IA injections is recommended, but not required. If not using ultrasound guided IA injection, then with a clinical IA injection, joint fluid must be identified within the needle hub before injection of 2% lidocaine (without epinephrine) and CNTX-4975-05. After injection of CNTX-4975, the knee joint will be passively flexed and extended 5 times over 1 minute to facilitate distribution of the CNTX-4975 within the knee. All subjects must be monitored for at least 30 minutes (or longer, as required by the protocol) after study drug injection to ensure that they do not have a hypersensitivity reaction/anaphylaxis.

The duration of cooling and the knee pain upon discontinuation of cooling must be entered into the electronic case report form [eCRF]. If cooling must be reapplied, the time and knee pain level must be recorded in the eCRF, and timing of subsequent pain assessments should be on the standard time lines in the eCRF.

Each site will be randomly assigned 1 of the following 5 treatment regimens to be employed for ALL subjects at that site:

Group	Cooling	• Pre-cool	Needle	Post-
	Device	• Lidocaine %		dose
		Post-lido cool		cooling
1. Breg Cooling Control Group	Breg ice water pump	

15 mins

2% lidocaine

30 mins

	Separate needles for lidocaine and CNTX-4975-05	30 to 90 mins as needed
2. Gel Pack Cooling Group	Elasto- Gel	

40 mins

2% lidocaine

10 mins

	Separate needles for lidocaine and CNTX-4975-05	10 to 90 mins as needed

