#### 13.4 Statistical Analyses

This section presents a summary of the planned statistical analyses. A statistical analysis plan that describes the details of the analyses to be conducted will be written prior to database lock.

Unless otherwise indicated, all testing of statistical significance will be two-sided, and a difference resulting in a p value of  $\leq 0.05$  will be considered statistically significant. To control for the overall type I error rate, hierarchical testing based on fixed sequence procedure will be used. If statistical significance is declared for the primary analysis, formal hypothesis testing will be done for the secondary endpoints until a non-significant result is reached. All other p values from secondary and exploratory endpoints, after a non-significant p value is reached, will be considered nominal.

For analyses involving study site, if the number of subjects per site is small, sites may be pooled for analysis, or omitted from statistical models. The final determination will be made prior to database lock.

Summary statistics will be provided for the variables described below. For continuous variables, these statistics will typically include the number of subjects, mean, standard deviation (SD), median, minimum, and maximum. For categorical variables, these statistics will typically include the number and percentage of subjects in each category.

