# 13.4.3.1 Primary Analysis

The primary analysis will compare each experimental treatment regimen to the Breg Cooling Control Group using an equally-weighted, combined score calculated from the following 3 measures: 1) pain 30 minutes after CNTX-4975-05 injection (using the 0-4 scale of none, mild, moderate, moderately severe, and severe), 2) SS with the treatment regimen; and 3) IS with the treatment regimen, all assessed on the index knee. Ratios of the mean values of test/control will have 95% confidence intervals constructed for each treatment regimen versus the Breg Cooling Control Group. For a treatment regimen to be considered clinically acceptable, it must be no more than 30% worse than the Breg Cooling Control Group and the lower limit of the 95% confidence interval for the treatment regimen must be greater than 0.7. This analysis will be performed on the ITT population.

For analysis, satisfaction scores (SS and IS) and 30 minute pain after CNTX-4975-05 injection will be transformed to equivalent scales, and 30 minute pain after CNTX-4975-05 injection will be reverse-scored so that higher scores represent lower pain, in order to have the 3 components on the same scale before they are combined by summing the 3 scores for a composite score. A sensitivity analysis will be performed that creates a composite score using the original scales (with the pain scores still reverse-scored to ensure the direction of the effect remains the same), using the ITT population.

All other continuous secondary and exploratory efficacy endpoints will be summarized using descriptive statistics by subject type, experimental treatment regimen, and week/visit, as appropriate, and analyzed using a mixed-model repeated measures (MMRM) analysis or by analysis of covariance, as appropriate. Categorical endpoints will be compared between treatments using Pearson's chi-square or Fisher's exact test, as appropriate.

Safety analyses will be conducted using data from the safety population.

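### The 0.7 acceptability rule is judged on all enrolled subjects alone, so nothing planned shows whether a favourable verdict depends on departures from the assigned regimen

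*Combined protocol and SAP*

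**What the plan says.** Section 13.4.3.1 (Primary Analysis) has two conditions for a regimen to be acceptable. The first limits the observed ratio: "it must be no more than 30% worse than the Breg Cooling Control Group". The second concerns its precision and sets the margin: "the lower limit of the 95% confidence interval for the treatment regimen must be greater than 0.7". The section then fixes the population: "This analysis will be performed on the ITT population".

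Section 13.3 lists only two populations. One is "Intent-to-Treat (ITT): all enrolled subjects". The other is "Safety: all subjects who receive any amount of planned CNTX-4975-05", which serves the safety analyses. Neither carries a condition on adherence to the regimen.

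One sensitivity analysis of the composite is stated: "A sensitivity analysis will be performed that creates a composite score using the original scales". It changes the scoring and stays on ITT. Section 13.4.1.2 has deviations summarized or listed, and section 13.4.2 says that no compliance measure is computed.

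The data for an adherence-based analysis are already required. In the Synopsis: "The duration of cooling and the knee pain upon discontinuation of cooling must be entered into the electronic case report form". Sections 9.11 and 13.4.2 also have injection procedure details recorded in the eCRF.

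Regimens are assigned by site (section 9.5), the study is open-label (section 9.6), and section 13.4 defers details to an SAP to be written before database lock.

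**The concern.** A lower-limit rule against a margin is a non-inferiority test. In such a test, anything that makes the two arms more alike works in favour of passing. A superiority test has the opposite property, which is why ITT alone is a cautious choice there and not automatically so here.

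The departures that matter come before or at the study-drug injection: pre-injection cooling time, cooling device, one needle or two, and lidocaine strength or volume. If some test-site subjects in effect receive control-like care on these points, they stay in the test arm under ITT and pull the ratio towards 1. A regimen that would fail if followed could then be called acceptable and taken forward as the recommended procedure.

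A second gap sits beside this. Enrolment is not defined as a point in time, and some enrolled subjects may never be injected: section 9.3.3 bars injection when guidance is not used and no joint fluid is aspirated, and the Schedule of Events puts drug and pregnancy tests before injection on Day 1. Such subjects have no 30-minute pain score, and no missing-data rule covers them.

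**Working it through.** **The plan's own figure.** Section 13.2 gives about 850 subjects, chosen for safety requirements. It states no power, SD, expected ratio or dropout, so 850 cannot be derived from the 0.7 rule.

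**Inputs from the plan.** Margin 0.7; 95% interval with "all testing of statistical significance will be two-sided", so 2.5% in the relevant tail for each regimen; about 850 subjects; five regimens; at most 45 concurrent sites (section 7.3).

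**Assumptions.** Equal arms, 850/5 = 170. Equal site sizes, 850/45 = 18.9 (section 7.3 expects about 18). SD of the composite equal in both arms, at CV = 0.25 of the control mean. ICC = 0.05. A share f of test-arm subjects depart and score like control. The documents give no value for CV, ICC or f.

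**Formulas.** R is the true ratio under full adherence.

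- Ratio seen in ITT: Ro = R + f(1 − R)
- Design effect: DE = 1 + (18.9 − 1) × 0.05 = 1.895
- SE = 0.25 × √(1.895/170) × √(1 + Ro²) = 0.0264 × √(1 + Ro²)
- P(accept) = Φ((Ro − 0.7)/SE − 1.96)

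**Example.** R = 0.70, f = 10%: Ro = 0.70 + 0.10 × 0.30 = 0.730; SE = 0.0264 × √1.533 = 0.0327; Φ(0.030/0.0327 − 1.96) = 0.149.

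| True R | f = 0 | f = 5% | f = 10% | f = 20% |
|---|---|---|---|---|
| 0.70: ITT ratio | 0.700 | 0.715 | 0.730 | 0.760 |
| 0.70: P(accept) | 2.5% | 7% | 15% | 44% |
| 0.65: ITT ratio | 0.650 | 0.6675 | 0.685 | 0.720 |
| 0.65: P(accept) | 0.02% | 0.1% | 0.8% | 9% |

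**Sensitivity.** For f = 10%, with CV from 0.15 to 0.35 and ICC from 0.02 to 0.10, P(accept) runs from 8% to 44% at R = 0.70 and from 0.2% to 1.3% at R = 0.65.

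**Share needed to reach the margin.** Setting Ro = 0.70 gives f = (0.70 − R)/(1 − R): 6% from 0.68, 14% from 0.65 and 25% from 0.60.

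**Departures in the other direction.** Take R = 0.75 and departers who score half the control value, so Ro = 0.75(1 − f) + 0.5f. At f = 0, 10% and 20% the ratio is 0.750, 0.725 and 0.700, and P(accept) falls from 33% to 12% to 2.5%. These departures make acceptance harder.

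**The case against.** A reader might infer that departures in general push a poor regimen towards acceptance. The documents do not support that. The direction depends on the kind of departure, and the plan states neither the rate nor the direction to expect. An incomplete lidocaine volume, for instance, could lower comfort and so lower the ratio.

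Nor should one infer that staff prolonging post-dose cooling, because a short regimen hurts, is the route. As-needed cooling up to 90 minutes is written into all five regimens, and oral pre-medication is at the investigator's discretion (section 9.3.1). Within the stated limits these are adherence, and a per-protocol set would keep those subjects. Pre-cooling, lidocaine and needle method all precede the pain after study drug, so that pain cannot cause departures in them for the same knee. Site-level assignment also limits wholesale switching to the control regimen.

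Uninjected subjects do not dilute the ratio. They contribute nothing to an observed-data mean and matter only if values are imputed. That is a missing-data gap.

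The remedy has a weakness too. If departers are selected on outcome, removing them biases the per-protocol result. Suppose the worst-scoring 10% of the test arm are excluded at R = 0.70, with normal scores. The mean rises by 0.25 × 0.1755/0.9 = 0.049, the ratio becomes 0.749, and, with n and SD held fixed, P(accept) in that set is about 32% where 2.5% is nominal.

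Finally, the promised SAP could still add such a set. All of this stands, and it narrows the point. The documents still contain no analysis by which an acceptable verdict could be checked against adherence.

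**Conclusion.** The gap is real. The acceptability rule is a non-inferiority rule resting on ITT alone, and no planned analysis tests whether its verdict depends on departures from the regimen. The bias is conditional: only departures that make the arms alike raise the ratio.

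Under the stated assumptions it matters for a regimen near the margin, where false acceptance is 7%, 15% or 44% at departures of 5%, 10% or 20%. It matters much less for one clearly below it: 0.1%, 0.8% or 9% at a true ratio of 0.65. The 44% should not be read as the trial's expected error rate, since it needs a true ratio exactly at 0.70 and 20% of test-arm subjects scoring fully like control. A supportive analysis should be added, because it is cheap and a requirement that both sets agree can only tighten the rule.

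**What to change.** 1. Keep the comparison by site-assigned regimen as primary. State that it uses injected subjects with a primary assessment, or state how enrolled but uninjected subjects are handled.
2. Prespecify a supportive per-protocol set: assigned device and needle method used, assigned lidocaine strength and full volume given, study drug given, and fixed cooling times and the 30-minute rating within window. As-needed post-dose cooling within the stated limits and permitted pre-medication do not exclude a subject.
3. Require the acceptability conclusion to be the same in both sets, and report the number and type of exclusions by regimen.
4. Fix this now, before any of the interim reviews that section 13.4.5 allows at about 20%, 50% and 75% completion. The study is open-label, so a set defined just before database lock could be shaped by visible results.
5. Before defining adherence, reconcile the regimen passages that conflict. The Synopsis text on injection without ultrasound names 2% lidocaine, while regimen 5 is assigned 1%. Regimen 5 has 45 minutes of pre-cooling, but its window refers to 40 minutes (Synopsis and section 9.3.2). The text for regimen 4 has a 10-minute minimum before cooling may be discontinued that its table row lacks.

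Cost: SAP wording and one extra run of the primary analysis on data already collected. Downsides: a smaller per-protocol sample and possible selection bias in it, which is why it supports the primary analysis and does not replace it.

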#### 13.4 Statistical Analyses

This section presents a summary of the planned statistical analyses. A statistical analysis plan that describes the details of the analyses to be conducted will be written prior to database lock.

Unless otherwise indicated, all testing of statistical significance will be two-sided, and a difference resulting in a p value of  $\leq 0.05$  will be considered statistically significant. To control for the overall type I error rate, hierarchical testing based on fixed sequence procedure will be used. If statistical significance is declared for the primary analysis, formal hypothesis testing will be done for the secondary endpoints until a non-significant result is reached. All other p values from secondary and exploratory endpoints, after a non-significant p value is reached, will be considered nominal.

For analyses involving study site, if the number of subjects per site is small, sites may be pooled for analysis, or omitted from statistical models. The final determination will be made prior to database lock.

Summary statistics will be provided for the variables described below. For continuous variables, these statistics will typically include the number of subjects, mean, standard deviation (SD), median, minimum, and maximum. For categorical variables, these statistics will typically include the number and percentage of subjects in each category.

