#### 7.3 Study Site(s)

The study will take place at no more than 45 concurrent sites in the US, Germany, Spain and the United Kingdom. Each site is anticipated to screen a sufficient number of subjects to be able to enroll approximately 18 subjects. A study site with an acceptable recruitment rate and acceptable quality metrics may be allowed to recruit more subjects if other sites have low enrollment.

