#### 9.5 Method of Assigning Subjects to Treatment Groups

All enrolled subjects will be assigned to CNTX-4975-05. Assignment to unilateral or bilateral injections will be determined by the subject's OA pain and previous joint replacement status. The subject's joint treatment regimen will be based on the site at which the subject is enrolled.

Unilateral or Bilateral Injections: The study population will contain 3 types of subjects, with a targeted minimum of 150 subjects of each type:

- 1. Subjects with unilateral or bilateral OA of the knee, with one knee (the index knee) with moderate to severe pain (K-L grade 1-4) and the other knee (the contralateral knee) with no to mild pain. These subjects will receive an IA injection in the index knee only.
- 2. Subjects with bilateral OA of the knees, with both knees having moderate to severe pain (K-L grade 1-4, with worse pain in the index knee). These subjects will receive an IA injection into each knee (1 week apart). The index knee in these subjects is the one with the worst pain with walking. Where both knees have equal pain with walking, then the knee on the subject's dominant side will be designated the index knee.
- 3. Subjects who have unilateral or bilateral OA of the knee, with one knee with moderate to severe pain (the index knee [K-L grades 1-4]) and previous PJR or TJR in the other knee (the contralateral knee). These subjects will receive an IA injection into the index knee only.

Joint Treatment Regimen: Each site will be randomly assigned 1 of the 5 joint treatment regimens to be employed for ALL subjects at that site. The joint treatment regimens are listed in Section 9.3.2.

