#### 9.6 Blinding and Unblinding Treatment Assignment

This is an open-label study.

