#### 13.4.5 Interim Analyses

To ensure that the benefit/risk ratio continues to be appropriate for the OA knee indication, interim analyses for a focused review of safety and efficacy may be performed when approximately 20%, 50%, and/or 75% of subjects have completed the trial. The output for the interim analyses will be consistent with the currently planned final analyses.

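### Section 13.4 lets small sites be pooled or omitted from models as late as database lock, which does not fit a design with one regimen per site; whether this touches the 0.7 rule depends on the SAP

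*Combined protocol and SAP*

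**What the plan says.** Section 13.4, for analyses involving study site, where few subjects are enrolled per site: "sites may be pooled for analysis, or omitted from statistical models. The final determination will be made prior to database lock". No number defines small, and nothing limits pooling to sites with the same regimen. It is also unclear whether a site is omitted by removing the site term or by removing that site's subjects. The SAP has the same deadline: "A statistical analysis plan that describes the details of the analyses to be conducted will be written prior to database lock".

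Section 9.5 on assignment: "Each site will be randomly assigned 1 of the 5 joint treatment regimens to be employed for ALL subjects at that site". Section 9.6: "This is an open-label study".

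Section 13.4.5 allows interim reviews of safety and efficacy at about 20%, 50% and/or 75% of completers: "The output for the interim analyses will be consistent with the currently planned final analyses". Section 12 states that there is no data safety monitoring board.

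Section 13.4.3.1 compares each regimen with the Breg control by a ratio of mean composite scores, on the ITT population. A regimen is acceptable if the lower 95% limit exceeds 0.7. That section names no site term and no adjustment for clustering. Section 13.3 defines ITT as every enrolled subject.

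**The concern.** A rule that allows small sites to be merged, or the site factor to be dropped, is ordinary in a trial that randomises subjects within sites. There, site is a nuisance factor and the treatment contrast survives its removal. Here site carries the randomisation, so each option in the clause acts on the regimen comparison itself:

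- **Site term dropped.** Subjects at one site share staff, an investigator who supplies one of the three composite components, and one regimen. Treating them as independent makes the interval too narrow.
- **Sites of different regimens pooled.** The block then contains a regimen contrast between subjects who were never randomised against each other. The block is also formed by enrolment, which happens after the site knows its regimen.
- **Sites' subjects dropped.** This departs from ITT as section 13.3 defines it.

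At stake are regimen comparisons whose standard error, and possibly estimate, depend on a choice left open until database lock. In an open-label study that deadline does not guarantee that the choice precedes sight of regimen results.

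**Working it through.** **Inputs from the protocol.** At most 45 concurrent sites, about 18 subjects each, with low enrolment at some sites foreseen (section 7.3); about 850 subjects (section 13.2); five regimens, one per site (section 9.5); lower 95% limit above 0.7 (section 13.4.3.1).

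**Inputs assumed.** Equal allocation, giving 45/5 = 9 sites and 850/5 = 170 subjects per regimen. ICC of 0.02, 0.05 or 0.10; the documents give none.

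**Plan figures.** 45 × 18 = 810, against 850; 850/45 = 18.9 per site. Both site figures are approximate, so this is not an error. I use 19 per site.

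**Step 1: nesting.** A design matrix of 45 site indicators has rank 45. Adding five regimen indicators leaves it at 45. Regimen therefore cannot be estimated beside fixed site effects unless pooling mixes regimens.

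**Step 2: effect of leaving site out.** Design effect = 1 + (19 − 1) × ICC. Effective size per regimen = 170 / design effect. At a true ratio of 0.7, an interval with nominal one-sided error of 2.5% that ignores site has false acceptance 1 − Φ(1.96 / √design effect).

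| Assumed ICC | Design effect | Effective n of 170 | False acceptance |
|---|---|---|---|
| 0.02 | 1.36 | 125 | 4.6% |
| 0.05 | 1.90 | 89 | 7.8% |
| 0.10 | 2.80 | 61 | 12.1% |

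These rates measure the effect of ignoring site. They say nothing about pooling.

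**Step 3: effect of choosing late.** A simulation used 4,000 runs per setting, true ratio 0.7, one regimen against control. Further assumptions: nine sites per regimen of 4 to 38 subjects (170 in all), control mean 70, SD 20, and the three smallest sites per regimen counted as small. The five site treatments are my own list: site ignored; site-level analysis; small sites dropped under either of these; small sites pooled within regimen.

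| Assumed ICC | Site ignored | Best of five chosen after the result |
|---|---|---|
| 0 | 2.2% | 5.2% |
| 0.02 | 5.5% | 8.1% |
| 0.05 | 9.3% | 11.5% |
| 0.10 | 13.7% | 16.4% |

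One site-level analysis fixed in advance, with all sites kept and a t reference, gave 1.9% to 2.4% across the same ICCs. Free choice adds about 2 to 3 points to ignoring site. The site-ignored rates exceed those in step 2 because site sizes are unequal here.

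**Step 4: pooling across regimens, a constructed case only.** Take two regimens, each with seven sites of 19 and two of 4 subjects (141 per regimen). Fit fixed site effects and merge the four small sites into one block. The regimen contrast then rests on 8 against 8 subjects: variance 1/8 + 1/8 = 0.25, against 2/141 = 0.0142 for the raw contrast, in units of residual variance. The ratio is about 18 at ICC 0. With between-site variance in both estimators it falls to about 14, 11 and 8 at ICC 0.02, 0.05 and 0.10. The documents state neither fixed site effects nor cross-regimen pooling, so this shows what the wording fails to exclude and is not an expected size.

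**The case against.** The strongest objection concerns reach. The clause applies only to analyses that involve site, and section 13.4.3.1 names no site term. Sections 13.4.3.1 and 13.4.3.2 allow MMRM or ANCOVA for other endpoints without listing site as a covariate. A reader might infer that the clause by itself undermines the 0.7 rule. The documents do not support that: it reaches the primary contrast only if the SAP brings site into that analysis. This stands.

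The rates in step 2 could also be read as caused by the clause. They would be, only if the starting plan adjusted for site, and none is stated. The absence of any clustering adjustment is a separate weakness, and the clause would permit it to persist in a model that did include site. This too stands.

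The 18-fold figure might be taken as the likely damage. It needs two choices that the documents do not make. It would also widen the interval and make 0.7 harder to clear, the opposite direction from ignoring clustering.

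Finally, a reader might infer that the site decision will be made to suit the results. Interims are optional, and the documents do not say who sees their output or whether any precedes the site decision. The ITT definition also favours reading omission as removal of the site term. All of this is fair, but none of it makes the wording suitable for a design in which site is the randomised unit.

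**Conclusion.** The concern holds in a limited form. The clause permits dropping site from models and pooling without a same-regimen limit, and neither suits site-level assignment. The nesting result follows from section 9.5 and needs no assumption about ICC or site size. The conflict between dropping subjects and ITT follows from section 13.3.

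The sizes are illustrative. False acceptance of about 4.6% to 12.1% applies where site is ignored, with 19 subjects at every site and ICC of 0.02 to 0.10. The further 2 to 3 points from late choice depend on the simulated layout and the five options listed. The variance ratio in step 4 should carry no weight as an estimate. Selection with results in view is possible under an open label, optional efficacy interims and a SAP due only by lock; nothing shows that it is planned. The sentence should be changed, but the documents do not establish that the primary conclusion is already compromised.

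**What to change.** In the SAP, replace the sentence with:

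> Regimen comparisons will keep all enrolled subjects and treat site as the cluster (random site effect or site-level summaries). Site will not be omitted from these models. Any pooling of small sites will be only among sites assigned the same regimen, with a stated size threshold and a stated fallback for non-convergence.

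The SAP should also say whether the primary ratio analysis is one of these comparisons. Finalise it before the first interim output by regimen or, if that has passed, before any further such output, and record the date.

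Cost: an earlier SAP sign-off, less modelling freedom, and wider intervals than an analysis that ignores site, by a factor of √1.36 = 1.17, √1.90 = 1.38 or √2.80 = 1.67 at ICC 0.02, 0.05 or 0.10. No subject or procedure is affected. The protocol sentence is permissive, so a SAP that declines the permission does not contradict it. Changing the protocol text as well would need a formal amendment with investigator signature and ethics approval (sections 14.8 and 15.3) across up to 45 sites, and is not essential.
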